Rationale for Study	
Despite recent advances in the treatment of mCRPC, including the approval of novel agents such as sipuleucel-T, abiraterone acetate, enzalutamide, and radium-223, patients with mCRPC have a poor prognosis and many eventually succumb to their disease. Patients with abiraterone and/or enzalutamide refractory mCRPC represents a particularly challenging subgroup of patients who have limited effective treatment options other than chemotherapy.
 
Prostate-Specific Membrane Antigen (PSMA) is a cell surface protein overexpressed on most prostate cancer cells, especially in advanced stage disease. The safety and efficacy of ¹⁷⁷Lu radiolabeled PSMA has been reported in several studies, including a recent prospective phase 2 study (Hofman et al. 2017). In patients with PSMA-avid metastatic disease, the PSA response proportion and objective response rate by RECIST 1.1 range from 40-60%, in heavily pre-treated patients. However the response duration is short, and therefore novel treatment strategies are needed to maintain and extend the duration of response achieved.
 
We propose to utilize immune checkpoint inhibition with pembrolizumab as a means to maintain anti-tumor response. We leverage a robust body of literature indicating that radiotherapy induces an immunogenic response, in the form of induction of infiltrating T cells, broadening of the T cell repertoire, and induction of PD-L1 expression, facilitating subsequent treatment with immune checkpoint inhibitor.
 
In the current study we will obtain the preliminary safety and efficacy data of ¹⁷⁷Lu-PSMA-617 radioligand therapy (RLT) in combination with pembrolizumab in patients with metastatic castration resistant prostate cancer. Favorable results with respect to toxicity and preliminary evidence of efficacy would form the basis for a subsequent definitive randomized study of the treatment combination in PSMA-expressing metastatic castration-resistant prostate cancer.

Primary Objectives	
Part A: To determine the recommended phase 2 dose and schedule of ¹⁷⁷Lu-PSMA-617 in combination with pembrolizumab in patients with mCRPC.
 
Part B (Dose Expansion): To determine the objective response rate by RECIST 1.1 criteria.

Secondary Objectives	
1. To characterize the safety profile of the combination2. To determine the median duration of response by RECIST 1.1 criteria.3. To determine the proportion of patients who experience $\geq 50\%$ decline from baseline in serum PSA.4. To determine the median PSA progression-free survival.5. To determine the median time to symptomatic skeletal related event.6. To determine the 6 month radiographic progression-free survival rate and median radiographic progression-free survival.7. To determine the median overall survival.
Correlative Objectives	
1. To assess the lesion-specific response rate by baseline PSMA avidity on ^{68}Ga-PSMA-11 PET.2. To quantify the change from baseline in T cell repertoire, circulating T cell subsets, tumor infiltrating lymphocytes, and tumor PD-L1 expression by immunohistochemistry after one priming dose of Lu-PSMA RLT.3. To explore the relationship between timing of the ^{177}Lu-PSMA-617 priming dose with initiation of pembrolizumab with respect to immunologic, safety, and efficacy outcomes.4. To descriptively characterize the patterns of uptake on ^{68}Ga-PSMA-11 PET at the time of disease progression.5. To explore relationship between tumor genomic profile with clinical outcomes including response rate and progression-free survival.6. To explore the relationship between tumor dosimetry with objective response.

Study Design	
This is a single-center Phase 1b open-label, study of PSMA-targeted radionuclide therapy with ^{177}Lu-PSMA-617 in combination with pembrolizumab in patients with mCRPC who have previously progressed on at least one prior androgen pathway inhibitor (e.g. abiraterone, enzalutamide, apalutamide). Patients must have at least three metastatic lesions which are PSMA-avid on baseline ^{68}Ga-PSMA-11 PET imaging.
 
In Part A of the study, patients will be enrolled sequentially into one of three treatment schedules with respect to timing of ^{177}Lu-PSMA-617 in relation to first dose of pembrolizumab (N = 6 patients per schedule):
 
Schedule 1) Priming dose of ^{177}Lu-PSMA-617 administered on Cycle 1 Day 1 followed by pembrolizumab 200 mg IV q 21 days starting Cycle 2 Day 1.
 
Schedule 2) Priming dose of ^{177}Lu-PSMA-617 administered concurrently with initiation of pembrolizumab on Cycle 1 Day 1.
 
Schedule 3) Priming dose of ^{177}Lu-PSMA-617 administered on Cycle 1 Day 1 following initiation of pembrolizumab on Cycle 1 Day -21.
 
The dose-limiting toxicity window will be Cycle 1 + Cycle 2 (i.e. 6 weeks following C1D1 administration of Lu-PSMA-617 across) in all three Schedule cohorts.
 
In Part A of the study, 6 patients will be enrolled to Schedule 1, then 6 patients to Schedule 2, and finally 6 patients will be enrolled to Schedule 3.
 
The starting dose of ^{177}Lu-PSMA-617 will be 7.4 +/- 15% GBq, which is the recommended phase 3 dose of the agent. If the DLT frequency attributable to Lu-PSMA exceeds 33% at any point after 6 evaluable patients have been enrolled in Part A, Dose Level -1 of ^{177}Lu-PSMA-617 will be investigated (4 Gbq +/- 15%) for the remainder of patients enrolled on study.
 
Using the data obtained in Part A, the recommended phase 2 dose and schedule of ^{177}Lu-PSMA-617 will be determined by the Principal Investigator using a combination of safety, efficacy, and immunologic effects of treatment from the first two cycles (and additional cycles of treatment when available).
 
In Part B of the study, an additional 25 patients will be enrolled at the recommended phase 2 dose and schedule to obtain additional safety, efficacy, and immunologic data pertaining to the treatment combination.

--------------	--

Number of patients	
Approximately 18 patients will be enrolled during Part A of the study. An additional 25 patients will be enrolled in Part B.
 
Total sample size: 43
 
Part A: N ~ 18 patients (6 patients per Schedule; 3 Schedules to be evaluated)
 
Part B: N ~ 25 patients

Duration of Therapy	Patients will be treated until disease progression per PCWG3/RECIST 1.1 criteria, confirmed by repeat scans performed \geq 4 weeks later, unacceptable toxicity, or patient withdrawal, whichever occurs first.
Duration of Follow up	Patients will undergo safety follow up visit approximately 30 days and 90 days following end of treatment visit.
Duration of study	The study is anticipated to accrue 2-3 patients per month for an estimated accrual period of 21 months. The study is expected to reach completion for analysis of primary and secondary endpoints approximately 36 months from first patient enrolled.
Study Drugs	
¹⁷⁷Lu-PSMA-617 is a PSMA-targeted radioligand that will be produced under Current Good Manufacturing Practice (CGMP) regulations. The priming dose of ¹⁷⁷Lu-PSMA-617 will be 7.4 +/- 15% GBq, which is the recommended phase 3 dose of the agent.
 
The planned dose schedules to be evaluated in Part A of the study include:
 
Schedule 1) Priming dose of ¹⁷⁷Lu-PSMA-617 administered on Cycle 1 Day 1 followed by pembrolizumab 200 mg IV q 21 days starting Cycle 2 Day 1.
 
Schedule 2) Priming dose of ¹⁷⁷Lu-PSMA-617 administered concurrently with initiation of pembrolizumab on Cycle 1 Day 1.
 
Schedule 3) ¹⁷⁷Lu-PSMA-617 administered on Cycle 1 Day 1 following initiation of pembrolizumab on Cycle 1 Day -21.
 
The cumulative safety data, including safety data beyond Cycle 2 where available, immunologic priming effects, along with efficacy and pharmacodynamic data, will be utilized to determine the recommended schedule of ¹⁷⁷Lu-PSMA-617 in combination with pembrolizumab.

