Despite the significant anti-tumor activity with Lu-PSMA RLT, there are several significant limitations of this approach as monotherapy: 1) There is significant **heterogeneity of PSMA expression**, both in analysis of individual circulating tumor cells as well as diagnostic PSMA PET imaging of metastatic lesions across individual patients, and 2) Within PSMA-avid lesions, there is a **limited duration of response**. In a recently presented prospective phase 2 study of Lu-PSMA, despite enriching for patients with more homogenous level of PSMA uptake on baseline PET imaging, the median PSA progression-free survival by PCWG criteria was only 6.3 months (95% CI 4.8 – 8.3), and median overall survival only 12.7 months. Nearly half of the 30 patients enrolled received less than the pre-specified 4 doses of Lu-PSMA treatment, for both toxicity-related reasons (hematologic, salivary gland) as well as rapid disease progression following initial response. The reasons for rapid disease progression include baseline heterogeneity of PSMA expression among disseminated tumor cells, leading to diffuse bone marrow involvement in a subset of patients. There is a clear and unmet medical need to merge the rapid anti-tumor responses achieved by Lu-PSMA RLT with a treatment that can both sustain and spread response to PSMA-negative lesions without excess cumulative toxicity.

Immune checkpoint inhibition, by virtue of antigen spread induced by immunogenic cell death induced by antecedent radioligand treatment, may accomplish this goal.

1.4 Immune Checkpoint Inhibition Leads to Durable Responses in a Minority of mCRPC Patients

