3.3 Eligibility Criteria

Patients must have baseline evaluations performed prior to Cycle 1 Day 1 of treatment and must meet all inclusion and none of the exclusion criteria. In addition, the patient must be thoroughly informed about all aspects of the study, including the study visit schedule and required evaluations and all regulatory requirements for informed consent. The written informed consent must be obtained from the patient prior to enrollment. The following criteria apply to all patients enrolled onto the study unless otherwise specified.

Inclusion Criteria

Part A:

- (1) The subject is able and willing to comply with study procedures and provide signed and dated informed consent.
- (2) Male participants who are at least 18 years of age on the day of signing informed consent.

(3) Histologically confirmed prostate adenocarcinoma. *De novo* small cell neuroendocrine prostate cancer will not be allowed due to putative lower PSMA expression in this tumor subtype. Treatment-emergent small cell neuroendocrine prostate cancer detected in metastatic tumor biopsy is not an exclusion.

(4) A minimum of three PSMA-avid lesions on baseline ^{68}Ga -PSMA-11 PET, with positive lesions defined as those with SUV_{max} values greater than liver.

(5) Progressive metastatic castration-resistant prostate cancer by PCWG3 criteria at the time of study entry.

(6) Castrate level of serum testosterone at study entry (< 50 ng/dL). Patients without prior bilateral orchiectomy are required to remain on LHRH analogue treatment for duration of study

(7) Prior progression on at least one second generation androgen signaling inhibitor including abiraterone, apalutamide, darolutamide, and/or enzalutamide.

(8) Adequate hematologic, renal, and liver function, defined as:

- Absolute neutrophil count $> 1.5 \times 10^9/\text{L}$
- Hemoglobin $> 9.0 \text{ g/dL}$
- Platelet count $> 100,000/\text{microliter}$
- Serum creatinine $\leq 1.5 \times \text{ULN}$ or estimated GFR $> 50 \text{ ml/min}$ by Cockcroft-Gault or 24 hour urine collection.
- Total bilirubin $\leq 1.5 \times \text{ULN}$. In patients with known or suspected Gilbert's disease, direct bilirubin $\leq \text{ULN}$.
- Aspartate aminotransferase and alanine aminotransferase $\leq 2.5 \times \text{ULN}$ ($\leq 5 \times \text{ULN}$ in patients with liver metastases).

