8.4.3 Analytic Plan for Correlative Endpoints

Lesion-specific response rate by baseline PSMA avidity on ⁶⁸Ga-PSMA-11 PET:

All target lesions on baseline cross-sectional imaging will be assessed for response (e.g. > 30% reduction in longest diameter) on subsequent imaging during the course of study. The median baseline uptake on Ga-PSMA-11 PET between responding versus non-responding lesions will be compared using Mann-Whitney test. In addition, Spearman's rank correlation will be used to compare baseline lesion uptake on Ga-PSMA-11 PET with percent change from baseline in longest tumor diameter on subsequent cross-sectional imaging on study.

Percent change from baseline in T cell repertoire, circulating T cell subsets, tumor infiltrating lymphocytes, and tumor PD-L1 expression by immunohistochemistry after one priming dose of Lu-PSMA RLT:

T cell repertoire will be estimated using Morasita's distance as previously described. Quantification of circulating T cell subsets and TILs will be performed using flow cytometry and immunohistochemical analysis of tumor tissue and whole blood, respectively. PD-L1 expression will be analyzed as the percentage of tumor cells with positive surface expression. Correlative testing may be performed at outside laboratory facilities (i.e. Strata Oncology). The percent change from baseline in these parameters will be reported using descriptive statistics (e.g. median, range, standard deviation). In an exploratory fashion, the study cohort will be dichotomized by those with percent change from baseline above and below median and efficacy outcomes will be compared between dichotomized subgroups using log-rank test for time-to-event endpoints (e.g. rPFS, duration of response) and Fisher's exact test for categorical variables (e.g. objective response rate, 6-month rPFS rate, PSA50 response rate).

Genomic Sequencing

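### Correlative objective 1 asks for a lesion response rate by PSMA avidity, but Section 8.4.3 specifies only association tests, so no rate is estimated in avid or non-avid lesions

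*Combined protocol and SAP*

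**What the plan says.** Correlative objective 1, worded identically in the Abstract and in Section 2.1, is "To assess the lesion-specific response rate by baseline PSMA avidity on" baseline PSMA PET. Section 1.3 lists uneven PSMA expression and short response as the two limits of radioligand monotherapy. It states the need for "a treatment that can both sustain and spread response to PSMA-negative lesions without excess cumulative toxicity" and adds that checkpoint inhibition, "by virtue of antigen spread induced by immunogenic cell death induced by antecedent radioligand treatment, may accomplish this goal". The Abstract is narrower and presents pembrolizumab "as a means to maintain anti-tumor response".

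Section 8.4.3 carries the objective's title. It first defines lesion response: "All target lesions on baseline cross-sectional imaging will be assessed for response (e.g. > 30% reduction in longest diameter) on subsequent imaging". It then gives two analyses. The first reads "The median baseline uptake on Ga-PSMA-11 PET between responding versus non-responding lesions will be compared using Mann-Whitney test". In the second, Spearman's "rank correlation will be used to compare baseline lesion uptake on Ga-PSMA-11 PET" with percent change in longest diameter. The section gives no response proportion by avidity class, no interval, no avidity cut-off and no allowance for several lesions in one patient.

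A cut-off does exist, in Section 3.3, inclusion 4: "A minimum of three PSMA-avid lesions on baseline" PET, where a positive lesion is one with SUVmax above liver. That criterion sets a floor on avid lesions and does not bar non-avid ones. The biopsy footnote to the Schedule 3 calendar (Section 5.4) expects that some patients will have non-avid lesions.

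**The concern.** The objective asks how often lesions respond, given their avidity. The plan asks how avid lesions were, given whether they responded. The reversed question can show that uptake and response are related, but it cannot say what share of non-avid lesions shrank.

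That share matters because the radioligand is expected to do least in these lesions, and Section 1.3 hopes that pembrolizumab will carry response to them. With no comparator arm, it is among the more informative lesion-level results the trial could report. As written, a reader of the final report would see a p-value and a correlation, and could not tell from either whether few or many non-avid lesions responded.

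**Working it through.** The plan states no power, alpha, lesion count or expected lesion response for this objective, so there is no figure of its own to reproduce.

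**1. What each analysis returns.** Let p_A and p_N be the response probabilities in avid and non-avid target lesions. The objective asks for p_A and p_N. The Mann-Whitney null says that uptake has the same distribution in responders and non-responders. If response does not vary with uptake within a class, that is the same as p_A = p_N, at any level. The test therefore cannot tell 50%/50% from 5%/5%. When p_A exceeds p_N, the expected direction is the same whether p_N is 5% or 20%. Spearman's coefficient has the same limits. Neither output can be converted into p_N.

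**2. How often the tests reject.** From the documents: 43 patients (Section 3.1) and at most 5 target lesions each (Section 7.1), a ceiling of 43 × 5 = 215 lesions. Assumed, because the documents are silent:
- 25 patients × 2 = 50, 25 × 3 = 75, or 43 × 3 = 129 lesions;
- 10–30% of lesions non-avid;
- p_A = 50% and p_N from 5% to 50%;
- two-sided 0.05, lesions independent, 1,000 runs per setting;
- log uptake relative to liver half-normal, above zero for avid lesions (SD 0.9) and below zero for non-avid lesions (SD 0.5);
- percent change in diameter normal with SD 25, its mean set in each class so that P(change ≤ −30) equals p_A or p_N.

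Percentage of runs rejecting, Mann-Whitney / Spearman:

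| Lesions | Non-avid | p_N 5% | p_N 20% | p_N 35% | p_N 50% |
|---|---|---|---|---|---|
| 50 | 10% | 16 / 30 | 8 / 13 | 7 / 7 | 5 / 6 |
| 50 | 20% | 40 / 77 | 21 / 30 | 8 / 10 | 4 / 5 |
| 50 | 30% | 71 / 95 | 36 / 52 | 12 / 17 | 4 / 4 |
| 75 | 10% | 26 / 45 | 13 / 18 | 7 / 9 | 5 / 5 |
| 75 | 20% | 59 / 89 | 31 / 45 | 12 / 14 | 5 / 4 |
| 75 | 30% | 85 / 99 | 48 / 72 | 15 / 21 | 5 / 6 |
| 129 | 10% | 36 / 62 | 17 / 27 | 9 / 11 | 4 / 6 |
| 129 | 20% | 82 / 98 | 48 / 70 | 14 / 21 | 5 / 6 |
| 129 | 30% | 98 / 100 | 72 / 91 | 24 / 35 | 5 / 5 |

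With 5% response in both classes (75 lesions, 20% non-avid), both tests reject in about 4% of runs. That matches the last column.

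**3. Sensitivity to lesion number.** A second model (45% response in avid lesions, none in non-avid, SUVmax-scale uptake) was run at several sizes. With 20% non-avid, Mann-Whitney rejects in 51–54% of runs at 60 lesions (three separate simulations), 78% at 100 and 90% at 129. With 10% non-avid the figures are 15–18%, 27% and 36%.

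**4. The missing estimate.** Exact 95% limits for x responders among n non-avid lesions are the 0.025 quantile of Beta(x, n − x + 1) and the 0.975 quantile of Beta(x + 1, n − x). For x = 0 the upper limit is 1 − 0.025^(1/n); with n = 12 this is 1 − 0.025^(1/12) = 26%. Other illustrations, with assumed counts: 0/8 gives 0–37%, 3/12 gives 5–57%, 3/15 gives 4–48% and 8/39 gives 9–36%. These limits treat lesions as independent, and clustering within patients would usually widen them.

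**The case against.** The strongest reply is that objective 1 does not mention spread, and Section 8.4.3 does not present its tests as tests of spread. Whether uptake relates to response is a fair correlative question, and Spearman's coefficient answers it without a cut-off that might leave few non-avid lesions. Spread is one of two aims, and the Abstract and Section 1.7 stress maintaining response. This stands as a limit on importance. It does not touch the mismatch: the objective is worded as a rate, and no rate is planned.

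Some stronger readings are tempting, and the documents do not support them:

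- **Success would appear as a null result.** That holds only if non-avid lesions respond as often as avid ones, although avid lesions also receive the radioligand. Under partial spread an association can remain.
- **The tests would miss a complete absence of spread about half the time.** That comes from one assumed setting, 60 lesions with 20% non-avid. At 129 lesions and the same mix, the miss rate is about 10%. A gradient of response with uptake among avid lesions, which the models leave out, could raise power further.
- **A direct rate would separate spread from no spread.** The intervals for 0/12 (0–26%) and 3/12 (5–57%) overlap, and the first contains 25%.
- **Response in non-avid lesions would demonstrate spread.** SUVmax not above liver does not mean no uptake, and Section 1.4 reports a 17% response rate to pembrolizumab alone in PD-L1-positive tumours. A single-arm trial cannot separate these explanations.

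**Conclusion.** The point holds as a gap between objective and analysis. Followed as written, Section 8.4.3 yields no response rate in either avidity class, and this conclusion rests on the text alone. The simulations add that neither kind of test result is readable for spread. A null result fits equal response, general failure or too few non-avid lesions. A significant result fits partial spread as well as none.

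How often each outcome would occur cannot be fixed from the documents. The Mann-Whitney range of 16–98% at 5% non-avid response shows how far it depends on lesion number and mix. The figures also assume independent lesions and no uptake gradient within a class. The objective is correlative, with no alpha, power or decision rule, so this is a worthwhile low-cost repair and does not threaten the primary endpoints or sample size.

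**What to change.** In Section 8.4.3, make the main descriptive analysis of objective 1 the proportion of target lesions meeting that section's lesion-response criterion, reported separately for PSMA-avid lesions (SUVmax above liver, as in inclusion 4) and non-avid lesions. Give each proportion a 95% confidence interval that allows for several lesions per patient, for example cluster-robust or from a bootstrap that resamples patients. Also report how many patients have at least one non-avid target lesion, and in how many of them such a lesion responded.

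State that response in non-avid lesions is consistent with spread but does not prove it, since pembrolizumab alone or low-level uptake could also produce it. Keep the Mann-Whitney and Spearman analyses as supportive.

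The cost is a paragraph of analysis-plan text and one table, from baseline PET and target-lesion measurements already planned. The drawback is that the non-avid interval will be wide if few such lesions are target lesions. That is possible, because eligibility requires only avid ones, and the plan should say so in advance.

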DSMC	Data and Safety Monitoring Committee
DSMP	Data and Safety Monitoring Plan
DTPA	diethylene triamine pentaacetic acid
ECOG	Eastern Cooperative Oncology Group
FDA	Food and Drug Administration
Gbq	Gigabecquerel
Glu-urea	Glutamate-urea
F-18	Fluorine-18
⁶⁸ Ga	Galium-68
GCP	Good Clinical Practice
Gy	Gray
HDFCCC	Helen Diller Family Comprehensive Cancer Center
HIPAA	Health Insurance Portability and Accountability Act (HIPAA)
ICF	informed consent form
ICH	International Conference on Harmonization
IND	investigational new drug application
INR	international normalized ratio
IRB	Institutional Review Board
IV	intravenous
LHRH	luteinizing hormone-releasing hormone
¹⁷⁷ Lu	Lutetium-177
mCRPC	metastatic castration resistant prostate cancer
MR	magnetic resonance
MRI	magnetic resonance imaging
NCI	National Cancer Institute
PAP	prostatic acid phosphatase
PCWG3	Prostate Cancer Working Group 3

List of Abbreviations

PD-L1	Programmed death receptor ligand - 1
PET	positron emission tomography
PFS	progression free survival
PR	partial response
PRC	Protocol Review Committee
PSA	prostate specific antigen
PSMA	Prostate specific membrane antigen
RECIST	Response Evaluation Criteria in Solid Tumors
RLT	Radioligand therapy
SAE	serious adverse event
SUV	standardized uptake values
TCR	T cell receptor
ULN	upper limit of normal

1 Introduction

